c. The waveform data will be synchronized and subject to data analysis at a later time, looking specifically at waveform changes in response to fluid resuscitation types, rates and volumes, response to fluid therapy, types of injuries, operative timing and management, length of ICU and hospital stay, as well as survival. These results will be compared to existing LBNP waveform data. LBNP is a laboratory model of human hemorrhage that redistributes intravascular volume to the pelvis and lower extremities, thereby inducing central hypovolemia

D. Data Analysis

[figure not shown]
- All analyses will be conducted using SAS for Windows vs. 9.3 (SAS Institute Inc., Cary NC, USA) on de-identified data. Outcome and effect variables that are not normally distributed will be either categorized or analyzed using non-parametric methods. Missing data will be managed during analysis using the method proposed by [name] et al.⁴
- 2. Randomization effectiveness: Effectiveness of randomization will be examined by comparing the two groups regarding demographic variables (age, gender), injury severity (Injury Severity Score, blunt versus penetrating mechanism), degree of shock (Field SBP, Field Heart rate, Field Hematocrit), and a field coagulation measure (Field INR). We will adjust all analyses of endpoints for the covariates showing different distribution (either statistically significant difference at p<0.05 or clinically significant difference as determined by the DSMB). Specifically, adjustment for these pre-specified, potential confounders will be performed using three different methods according to the type of endpoint:

 - a. Categorical variables: we will use multiple logistic regression (polytomous logistic regression will be used for non-binary variables);
 - b. Continuous normally distributed endpoints: we will utilize mixed linear models to adjust for confounders, assuming an unstructured covariance structure.
 - c. Continuous non-normally distributed endpoints: if the endpoint is nonnormally distributed, we will attempt first to transform the variable to approximate normality (e.g., log transformation), and if this fails, we will resort to categorization based on previously determined, clinically relevant cutoffs.⁷⁹⁻⁸³

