Based on the interim analyses, a proposed new sample size is: with 80% power, 95% confidence and assuming mean admission lactate=5 mg/dL with standard deviation of 2 in the control group (based on the second interim analyses data), with 5 interim analyses (4 interim and 1 final, of which 3 already occurred), we will require 112 patients in each group (assuming the attrition rate observed in this RCT of 12%) to detect a difference of 1 mg/dL between the two mean lactates. This results in a total of 224, which corresponds to an increase of 74 patients over the current sample size of 150 patients.

G. Exploratory analyses

- Exploratory analysis 1: 24-hour mortality Based on the control arm of the recent ROC trial⁶⁷ and our trauma registry data, the control group 24-hours mortality is estimated to be between 19% and 26%.
 - a. **Definition:** 24-hours mortality is defined as death within 24 hours post injury (death of any cause). Research coordinators will verify the vital status of all patients 24 hours postinjury and determine the time of death in relationship to injury.
 - b. **Hypothesis:** 24-hour mortality will be significantly higher^{***} in control patients compared to experimental group patients.
 - c. Statistical test: Logistic regression will be used to compare the 24-hour mortality in the two groups. Statistical significance will be evaluated at each interim analyses for the primary outcomes and p-values, as well as 95% and 99% confidence intervals will be reported to the DSMB for analyses. If adjustment for pre-defined confounders is needed, we will use the above-defined method for categorical, binary variables. Time from injury to death will be evaluated using the Kaplan Meyer curves, which will be compared using SAS PROC LIFETEST. We will use the Wilcoxon test (which places more weight on shorter survival times) and the log-rank test (which privileges longer survival times). SAS PROC LIFETEST also constructs statistics to test for

^{***} Although the hypothesis is worded as "lower", all tests will be two-tailed to control for differences in either direction (higher or lower than the other group).

association between covariates and the lifetime variable through rank tests for the association of survival time with covariates, if there are potential confounders detected using the above-described procedures.

2. Pre-planned subgroup analyses:

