- 2. Statistical test: Kaplan Meyer curves will be compared using SAS PROC LIFETEST, which provides nonparametric k-sample tests based on weighted comparisons of the estimated hazard rate of the individual population under the null and alternative hypotheses. A variety of tests can be specified, of which we will use the Wilcoxon test (which places more weight on shorter survival times) and the log-rank test (which privileges longer survival times). SAS PROC LIFETEST also constructs statistics to test for association between covariates and the lifetime variable through rank tests for the association of survival time with covariates

H. Missing data prevention and treatment procedures:

We will follow the recommendations for prevention and treatment procedures outlined in the recent report by the National Research Council Panel on Handling Missing Data in Clinical Trials.⁸⁴ Missing data prevention is crucial in the primary endpoint to avoid any reduction in statistical power and the need for statistical analyses to account for the missing data. To minimize bias by missing data, research coordinators will collect data on the primary and secondary endpoints of all patients who were randomized in the field (including vital status at day 28 postinjury), including data on those patients who did not complete the protocol or were excluded for protocol violations or other reasons. Patients who withdraw from the study will be asked to allow research coordinators to collect SOC data from their medical record and, at a minimum, to provide contact information (and permission to be contacted) for verification of the primary endpoint mortality.

Based on previous trials in our institution, we predict that mortality will be missing due to loss of follow up in less than 2% of the sample. This is comparable to the loss to follow-up observed in the ROC trial (2 out 895 field-randomized patients). Several prevention procedures are in place to prevent missing data in our institution. At least two other data collection mechanisms (in addition to the COMBAT trial) will be capturing data from these patients: the Trauma Registry and the COMBAT/Trauma Activation database, which include information on the primary and secondary endpoints for COMBAT-eligible patients.

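### The plan promises covariate adjustment of all endpoint analyses but names no method for time to death or time to first RBC; the covariate rank tests it describes leave the arm comparison unadjusted

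*Combined protocol and SAP*

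**What the plan says.** IV.D.2 (Randomization effectiveness) states: "We will adjust all analyses of endpoints for the covariates showing different distribution". The trigger is a between-arm difference at p<0.05 or one that the DSMB judges clinically significant. IV.D.6 repeats the commitment. IV.D.2 then says that "adjustment for these pre-specified, potential confounders will be performed using three different methods according to the type of endpoint": logistic regression for categorical endpoints, mixed linear models for continuous normal endpoints, and transformation or, failing that, categorization for continuous non-normal endpoints.

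IV.G.1.c covers 24-hour mortality in two forms. The binary form uses logistic regression and has its own provision: "If adjustment for pre-defined confounders is needed, we will use the above-defined method for categorical, binary variables". For the time-to-event form, "Time from injury to death will be evaluated using the Kaplan Meyer curves, which will be compared using SAS PROC LIFETEST", with Wilcoxon and log-rank tests. The confounder provision for that form is "rank tests for the association of survival time with covariates, if there are potential confounders detected using the above-described procedures".

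IV.G.5.c covers time to first RBC: "Kaplan Meyer curves will be compared using SAS PROC LIFETEST, which provides nonparametric k-sample tests", again with Wilcoxon and log-rank tests. It adds that "SAS PROC LIFETEST also constructs statistics to test for association between covariates and the lifetime variable through rank tests", but does not say when these would be used or that they respond to confounding.

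**The concern.** A promise to adjust an analysis is met only if the plan names a procedure that returns an adjusted arm effect, p-value or interval. For these two outcomes it names none. If an imbalance were declared, an analyst following the text would run the covariate rank tests, learn whether each covariate is associated with the outcome, and still report unadjusted arm comparisons.

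Time to first RBC is where this matters most. IV.G.5.c singles it out as important to the funder. The November 2016 addendum treats it as a secondary objective and lists it among the promising trends, while noting that the survival analysis did not reach significance. IV.I.1.c allows significant exploratory results to count toward calling the therapy promising. IV.N.4 concedes that unblinded clinicians may time transfusions differently by arm, so this outcome already carries one source of bias.

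**Working it through.** **Step 1. Provisions side by side**

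| Analysis | Arm comparison | Adjustment named |
|---|---|---|
| 24-hour mortality, binary (IV.G.1.c) | Logistic regression | Logistic regression with covariates |
| Time to death (IV.G.1.c) | Log-rank, Wilcoxon | Rank tests of covariates, if confounders are detected |
| Time to first RBC (IV.G.5.c) | Log-rank, Wilcoxon | None; rank tests of covariates described, with no confounder clause |

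No Cox model and no covariate-stratified log-rank test is specified for either time-to-event analysis. The non-normal route in IV.D.2 is not a substitute. The addendum reports transfusion in 55% and 61% of the two groups, so 100 − 61 = 39% to 100 − 55 = 45% had none. Transforming the times does not deal with censoring, and categorizing them changes the endpoint.

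**Step 2. What the rank test does**

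Without ties, the arm log-rank statistic is U²/V, with U = Σ(g − p) and V = Σp(1 − p) summed over events. Here g is the arm indicator of the patient with the event and p is the proportion of the risk set in that arm. The covariate rank test has the same structure with the covariate in place of g. Neither statistic contains the other variable, so the covariate result cannot change the arm result. An adjusted version computes U and V within each covariate level and uses (ΣU)²/(ΣV).

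**Step 3. Size, by illustration**

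The documents give no power or event count for either analysis, so there is no plan figure to reproduce. The following simulation assumes no arm effect.

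- From the documents: 112 per arm; event proportions of 19% and 26% (the IV.G.1 estimate for 24-hour death), 12% (mortality assumed in the addendum) and (55 + 61)/2 = 58% (transfusion, as a proxy for first RBC); imbalance trigger p<0.05.
- Assumed: exponential times censored at a fixed horizon; one binary covariate with 50% prevalence and hazard ratio 2, 3 or 4; nominal two-sided 0.05 without interim boundaries; no competing death in the RBC case.
- Only simulated trials meeting the trigger were kept, 4,000 per scenario. The Monte Carlo standard error near 5% is √(0.05 × 0.95/4000) = 0.3 points.

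False-positive rate given a declared imbalance:

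| Event proportion | Plain log-rank, HR 2 / 3 / 4 | Stratified log-rank, HR 2 / 3 / 4 |
|---|---|---|
| 12% | 5.8 / 6.7 / 7.3% | 4.9 / 4.9 / 5.2% |
| 19% | 6.0 / 7.3 / 8.9% | 4.8 / 5.3 / 5.1% |
| 26% | 6.5 / 8.5 / 10.2% | 5.7 / 5.3 / 5.4% |
| 58% | 8.5 / 13.0 / 17.9% | 4.7 / 4.6 / 4.9% |

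Without conditioning on imbalance (8,000 trials, hazard ratio 3, 26% events), the plain test rejected in 5.1% and the stratified test in 5.2%. The Wilcoxon test was not simulated.

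**The case against.** The strongest reply is that the plan is underspecified rather than wrong. PROC LIFETEST can give an adjusted arm test, by stratifying on the confounder with arm as the group or by entering arm jointly with the covariates. It is true that the named software suffices. But the plan specifies neither set-up, and the procedure it does describe is a test of the covariates.

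Second, the link between detected confounders and rank tests is explicit only in IV.G.1.c. That stands. For time to first RBC, the defect is that no adjustment is named despite the general promise; the text does not say that confounding will be handled by rank tests there.

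Third, both analyses are exploratory in a Phase 2 trial. That also stands and limits the severity.

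Three stronger readings are tempting, and the documents do not support them:

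- A reader might infer that early mortality goes unadjusted. It does not: the binary 24-hour analysis has logistic adjustment, and only its time-to-event companion lacks it.
- A reader might infer a general type I error failure. The plain log-rank test is valid averaged over all randomizations; the excess appears only after conditioning on a declared imbalance.
- A reader might use the mortality gradient by field SBP in Table 2 to convert an imbalance into points of mortality and set that against the 10-point target. Table 2 gives registry mortality, not labelled as 24-hour mortality or as time to death. The target belongs to 28-day mortality, which already has logistic adjustment. The table says nothing about time to first RBC.

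**Conclusion.** The point holds as an undelivered commitment. IV.D.2 promises adjustment of all endpoint analyses and supplies no method for censored times. The only step given for time to death does not adjust the arm comparison, and time to first RBC has no adjustment named. The primary endpoint and the numbered secondary endpoints in IV.E and IV.F are not affected.

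The size depends on covariate strength and prevalence, which the documents do not give. For 24-hour death the illustrated rate is 5.8% to 10.2%. The low end is more plausible if the observed mortality of 12% to 13% persists, since deaths by 24 hours are a subset of those by 28 days. For first RBC it is 8.5% to 17.9%, and the top of that range needs an assumed hazard ratio of 4 at 50% prevalence. Severity is minor to moderate, resting mainly on the weight that the plan gives to time to first RBC.

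**What to change.** Add a fourth entry to IV.D.2 for censored time-to-event endpoints, and cite it in IV.G.1.c and IV.G.5.c in place of the covariate rank tests. It should specify a Cox model with arm plus the imbalanced covariates, reporting the adjusted hazard ratio and its confidence interval. Where the imbalance involves only one or two categorical factors, such as sex or injury mechanism, a log-rank test of arm stratified by those factors is an alternative. Most of the listed covariates (age, Injury Severity Score, field SBP, heart rate, hematocrit, INR) are numeric, so the Cox model will usually be needed. The entry should limit the number of covariates: at 12% mortality in 224 patients there would be only about 0.12 × 224 = 27 deaths by day 28, and no more than that by 24 hours. The unadjusted log-rank and Wilcoxon tests can stay alongside.

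The cost is a few sentences of analysis-plan wording, with the same data and the same software package. The wording should be fixed before the next analysis of the data.

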Table 2 below shows the number of patients received by our trauma center from Jan 2009-Dec 2010, by different eligibility criteria and respective mortality rates. These numbers exclude patients who died within 10 minutes of arrival (a group of patients with potentially unsalvageable injuries). These are conservative estimates;

our trauma volume has increased over 20% in 2012 and we anticipate maintaining this growth.

Table 2. Trauma registry data Jan 2009-Dec 2011 (3 years), excludes DOA (patients who died within 10 minutes of arriving at ED)

V		
Field Entry Criteria	Ν	Mortality
SBP<90	241	24%
SBP<80	175	32%
SBP≤70 OR (SBP 71-90 + HR≥108)	172	31%
SBP<70	109	44%

5. Gender, race, ethnic origin restrictions: There are no subject restrictions based upon gender, race, or ethnic origin unless the patient has a known objection to blood products. The research design will include sufficient enrollment of persons of both genders and diverse racial/ethnic backgrounds to ensure that the benefits and burdens of research participation are distributed in an equitable manner. There are no religious restrictions, but people of the faith of Jehovah's Witnesses typically object to transfusion of blood products and will be excluded from the study.

B. Detailed description of study design:

1. Procedure for enrollment, randomization and intervention:

- a) Determination of eligibility of enrollment in this stage is based on initial vital signs from EMS in the field. (See Population to be Enrolled-Section IV.A.4 and Paramedic Training-Section IV.J)
- b) Trained paramedics will look for opt out specific bracelets or necklace ID. If any of these opt out items are found or there is evidence of refusal of blood products, then the patient will not be enrolled.
- c) If a family member is present at the scene and not in shock or severely injured, easily accessible to paramedics, and the patient is not in imminent danger of death, the paramedics will state "We are enrolling him/her in a study where we are giving plasma for its clotting factors. We cannot explain the study at this time. Is this okay?" The paramedics will not be able to look for family members among a crowd of bystanders given the acute setting and the importance of transporting the patient to the hospital as soon as possible.

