Sample sizes of 60 and 60 achieve 80% power to detect a difference of 0.25 between the group proportions at a significance level (alpha) of 0.050000 using a two-sided test. These results assume that 3 sequential tests are made using the O'Brien-Fleming spending function to determine the test boundaries.

Bound	aries (Bn	dry) for data l	ooks					
Details	when Sp	ending = O'Br	ien-Fleming,	N1 = 60, N2 =	=60, P1 = 0.25	P2 = 0.50		
		Lower	Upper	Nominal	Inc	Total	Inc	Total
Look	Time	Bndry	Bndry	Alpha	Alpha	Alpha	Power	Power
1	0.33	-3.71030	3.71030	0.000207	0.000207	0.000207	0.018650	0.018650
2	0.67	-2.51142	2.51142	0.012025	0.011890	0.012097	0.398801	0.417451
3	1.00	-1.99302	1.99302	0.046259	0.037903	0.050000	0.382549	0.800000
Details	when Sp	ending = O'Br	·ien-Fleming,	N1 = 68, N2 =	=68, P1 = 0.27	P2 = 0.50		
	-	Lower	Upper	Nominal	Inc	Total	Inc	Total
Look	Time	Bndry	Bndry	Alpha	Alpha	Alpha	Power	Power
1	0.33	-3.71030	3.71030	0.000207	0.000207	0.000207	0.018650	0.018650
2	0.67	-2.51142	2.51142	0.012025	0.011890	0.012097	0.398801	0.417451
3	1.00	-1.99302	1.99302	0.046259	0.037903	0.050000	0.382549	0.800000
Details	when Sp	ending = O'Br	·ien-Fleming,	N1 = 75, N2 =	=75, P1 = 0.28	P2 = 0.50		
	•	Lower	Upper	Nominal	Inc	Total	Inc	Total
Look	Time	Bndry	Bndry	Alpha	Alpha	Alpha	Power	Power
1	0.33	-3.71030	3.71030	0.000207	0.000207	0.000207	0.018650	0.018650
2	0.67	-2.51142	2.51142	0.012025	0.011890	0.012097	0.398801	0.417451
3	1.00	-1.99302	1.99302	0.046259	0.037903	0.050000	0.382549	0.800000

Addendum November 16, 2016

Based on the interim analyses, a proposed new sample size is: with 80% power, 95% confidence and assuming mean admission TEG G = 7 dynes/cm2 with standard deviation of 3 in the control group (based on the second interim analyses data), with 5 interim analyses (4 interim and 1 final, of which 3 already occurred), we will require 112 patients in each group (assuming the attrition rate observed in this RCT of 12%) to detect a difference of 1.1 dynes/cm2 (from 7 to 5.9 dynes/cm2) between the two mean TEG Gs. This results in a total of 224, which corresponds to an increase of 74 patients over the current sample size of 150 patients.

4. Secondary Objective 4: To determine if early administration of plasma in the field will improve the incidence of early postinjury acidosis compared to the current standard of care.

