- a. **Blunt trauma mechanism:** There is evidence to suggest that the coagulation and inflammatory responses to injury differ by trauma mechanism, as they cause different tissue damage.^{101, 102}
 - 1. **Hypothesis:** Blunt trauma patients will have different effect sizes than penetrating trauma victims regarding the primary endpoint and secondary endpoints
 - 2. **Statistical tests:** Same tests described for primary and secondary endpoints stratified by mechanism of injury (blunt vs. penetrating). We will compare the 95% confidence intervals to determine overlap between the blunt and penetrating groups for each endpoint.
- b. Absence vs. presence of serious traumatic brain injury (TBI): there is evidence to suggest a differential coagulation and inflammatory response by the presence of TBI.^{101, 103, 104}
 - Hypothesis: Patients with associated TBI (defined as Abbreviated Injury Score, AIS, for Head >3) will have different effect sizes than their counterparts without TBI regarding the primary endpoint and secondary endpoints.
 - Statistical tests: Same tests described for primary and secondary endpoints stratified by presence of TBI. We will compare the 95% confidence intervals to determine overlap between the two groups for each endpoint.
- c. Presence of very severe hemorrhagic shock (HS, defined as SBP≤70 mmHg) versus severe HS (defined as SBP 71-90mmHg + Heart rate>=108bpm): There is evidence that the patients with very severe HS shock are more likely to require massive transfusion and present severe coagulopathy, thus potentially having differential mortality.¹⁰⁵
 - Hypothesis: Patients with very severe hemorrhagic shock (defined as SBP≤70mmHg) will have different effect sizes than their counterparts with severe hemorrhagic shock (defined as SBP 71-90mmHg +heart rate>=108bpm) regarding the primary endpoint and secondary endpoints.
 - Statistical tests: Same tests described for primary and secondary endpoints stratified by degree of hemorrhagic shock. We will compare the 95% confidence intervals to determine overlap between the two groups for each endpoint. Overall experiment error will be adjusted for the number of subgroups being analyzed using the Bonferroni method.

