- 1. Assessing Phase 2 trial results for promising benefits of the therapy: Because the trial has low power for the primary endpoint and some of the secondary endpoints, it is unlikely that we can detect a statistical significant difference. Thus, it is important to pre-determine the findings that we believe will indicate promising results that must be further investigated in larger Phase 3 trials. We will specifically look at the following measures to declare that the therapy is promising:
 - a. Statistical significant difference in primary endpoint or secondary endpoints
 - b. Strong, yet not statistically significant association (e.g., p-value = 0.10 to 0.05) with improved primary and secondary endpoints. The direction

of the association must indicate therapy benefit in ALL primary and secondary endpoints. Associations indicating harm will be reviewed by the DSMB for possible early termination.

c. Exploratory analyses of variables with supporting evidence for association with improved patient outcomes with statistically significant results (respecting the boundaries determined by the interim analyses methods, and adjusted for multiple comparisons as detailed in the description of the exploratory analyses).

The DSMB will also be in charge to making recommendations regarding the promising nature of the therapy and whether Phase 3 trials are warranted.

2. Interrupting the trial early:

The DSMB will be responsible for making a recommendation for early stopping of the trial. The DSMB will be asked to address early termination during each and every time they are activated, as described in the DSMB roles and responsibilities. In brief, the DSMB will be activated in case of a unanticipated problem, or during the interim analyses. Drs. [name] and [name] will prepare the materials for DSMB review containing:

- a. blinded results (experimental and control groups will be referred as A and B) of effectiveness of randomization, primary and secondary outcomes, as well as exploratory analyses (most especially the two subgroup analyses regarding blunt versus penetrating mechanism, presence of traumatic brain injury and Field SBP≤70mmHg versus SBP 71-90mmHg), any potential adverse events, and missing data description (to include number missing and their characteristics regarding outcomes and covariates).

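### Subgroup differences are judged by overlap of two 95% confidence intervals, which is not a 5% test of interaction and can miss real effect modification

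*Combined protocol and SAP*

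**What the plan says.** The subgroup analyses sit under "G. Exploratory analyses", in section IV.G.2. Each of the three factors (blunt or penetrating mechanism; serious brain injury or none; field SBP of 70 mmHg or less against 71-90 mmHg with tachycardia) carries a hypothesis that effect sizes differ between strata on the primary and secondary endpoints. The method is the same each time. The planned tests are repeated within strata and the intervals are then compared. For mechanism: "We will compare the 95% confidence intervals to determine overlap between the blunt and penetrating groups for each endpoint". For brain injury and for shock: "We will compare the 95% confidence intervals to determine overlap between the two groups for each endpoint".

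Under the shock item only, the plan adds: "Overall experiment error will be adjusted for the number of subgroups being analyzed using the Bonferroni method". It does not give the number of subgroups, and does not say whether the correction applies to the interval level or to the tests within strata.

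Section IV.I.2.a lists these results among the materials for the DSMB: "most especially the two subgroup analyses regarding blunt versus penetrating mechanism, presence of traumatic brain injury and Field SBP≤70mmHg versus SBP 71-90mmHg". That sentence announces two analyses and names three.

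**The concern.** A hypothesis that effect sizes differ is a statement about an interaction. It calls for an estimate of the difference between the stratum effects and a test of that difference. Neither is planned. The only interaction shown in the documents is randomisation by time for LY30, in the November 2016 addendum to section IV.E, and that is not a subgroup test.

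Checking whether two 95% intervals overlap is a different rule, with an error level that nobody chose and that shifts with the balance of the strata. The plan also does not say what overlap will be taken to show, which leaves room to read it as absence of a difference. At stake is how sensitive and interpretable the subgroup results are when the DSMB sees them. The primary conclusion is not at stake.

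**Working it through.** The plan gives no error level or power for the overlap rule, so there is no figure to reproduce. The check uses normal theory for two independent stratum estimates with standard errors SE1 and SE2, and r = larger/smaller.

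**Thresholds**
- Overlap rule: intervals separate when |difference| > 1.96(SE1 + SE2).
- Direct 5% test: rejects when |difference| > 1.96√(SE1² + SE2²).
- In standard units, separation needs z = 1.96(1 + r)/√(1 + r²).

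**Level and power of the overlap rule.** Power is taken at the interaction that a direct 5% test detects with 80% power (mean z = 1.960 + 0.842 = 2.802).

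| r | z needed | two-sided level | power |
|---|---|---|---|
| 1 | 2.772 | 0.0056 | 51% |
| 2 | 2.630 | 0.0085 | 57% |
| 3 | 2.479 | 0.013 | 63% |

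**Direct test with Bonferroni, same interaction.** The count is not stated, so a range is shown.
- Factor 2: critical z 2.241, power 71%.
- Factor 3: critical z 2.394, power 66%.
- Factor 6: critical z 2.638, power 56%.

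If the correction were instead put on the intervals (98.3% for a factor of 3), separation at r = 1 would need z = 3.386, giving level 0.0007 and power 28%. The plan does not say this will be done.

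**Example 1: TEG G, shock subgroup**
- SD 3, from the section IV.F.3 addendum ("assuming mean admission TEG G = 7 dynes/cm2 with standard deviation of 3 in the control group"); 112 per arm.
- Assumed split: Table 2 has 109 patients in the SBP<70 row and 172 in the entry-criteria row, so 109/172 = 0.634. The row labels differ slightly (<70 against ≤70), and the enrolled cohort may differ from the registry.
- Per arm: 112 × 0.634 = 71 and 41. SE = 3√(2/71) = 0.504 and 3√(2/41) = 0.662. So r is about 1.3, and the overlap rule has level 0.0060 (z 2.746).
- SE of the difference in effects = √(0.504² + 0.662²) = 0.832.
- Assumed difference in effects 2.2 dynes/cm², twice the 1.1 design difference: z = 2.2/0.832 = 2.64.
- Power: direct 75%, Bonferroni-3 60%, overlap 46%.
- With 98 evaluable per arm (112 × 0.88): 70%, 53%, 39%.
- With a difference of 1.1 and 112 per arm (z = 1.32): 26%, 14%, 8%.

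**Example 2: mortality**
- Assumed 12% against 2% in one stratum, 12% against 12% in the other, and a 50/50 split, so 56 per arm per stratum.
- Risk-difference scale: SE = √((0.12×0.88 + 0.02×0.98)/56) = 0.0473 and √(2×0.12×0.88/56) = 0.0614; z = 0.10/0.0775 = 1.29. Power 25%, 13%, 7% (direct, Bonferroni-3, overlap).
- Log-odds scale (Wald), same inputs: about 36%, 21%, 14%.
- The 2% cell expects about one death (56 × 0.02 = 1.1), so both sets are rough.

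**The case against.** The strongest reply is that this is a conservative rule in an exploratory section of a Phase 2 trial that concedes its own limits: "Because the trial has low power for the primary endpoint and some of the secondary endpoints". The rule does not inflate false positives, and no stopping or Phase 3 criterion names interval overlap. Three factors across eight endpoint hypotheses make 24 contrasts. With no true interactions, the expected number of false signals is 24 × 0.05 = 1.2 for unadjusted tests, 24 × 0.0167 = 0.40 with Bonferroni-3, and 0.13 to 0.32 with overlap (levels 0.0056 to 0.013). A strict screen has some merit.

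The comparison with 80% also flatters the direct test, since the plan already intends Bonferroni. Like for like at equal standard errors, the gap is 66% against 51% at a factor of 3 and 56% against 51% at 6. The TEG G example uses a large interaction; at half that size, both approaches usually miss it. Finally, the November 2016 addendum says three of the five analyses had already taken place, so a more sensitive test now would be a change made after data were seen.

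All of this stands, and it limits the severity. It does not rescue the method. Strictness that depends on stratum balance is not a chosen error rate, and overlap gives no estimate of how far the effects differ. When power is low, an interaction estimate with its interval is worth more than a yes-or-no reading of overlap.

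**Conclusion.** The concern holds. The subgroup hypotheses are about interaction, and the stated method does not test interaction at a known level. With standard errors within a factor of three of each other, the overlap rule works at 0.0056 to 0.013 and has 51% to 63% power where a direct 5% test has 80%. The loss against a Bonferroni-adjusted test is smaller, and at a factor of 6 there is no clear gain in power; the benefit is then an interpretable estimate at a stated level. The figures rest on independent, approximately normal stratum estimates and on assumed splits, and are least reliable for mortality. The consequence is a less sensitive and less interpretable exploratory result, with no threat to the primary analysis. The plan should be changed, but nothing else depends on it.

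**What to change.** - For each subgroup factor and endpoint, fit one model with arm, subgroup and their interaction: linear for continuous endpoints, logistic for binary ones, with an exact or penalised fit where deaths are sparse.
- Report the interaction estimate, its 95% interval and p-value.
- Apply the planned Bonferroni correction to those p-values and state the count. Reconcile it with section IV.I.2.a, which says two and lists three.
- Show stratum estimates and intervals as description only, and state that overlap is not evidence against interaction.
- State that power for interaction on mortality will be low, and low for continuous endpoints too unless the effects differ widely.
- Date the amendment and record which interim analyses preceded it.

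The cost is one sentence in each of the three subgroup paragraphs, a one-word correction in section IV.I.2.a, one extra term in regression models of a kind already planned, and a dated justification. No new data are needed.
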